#### Humoral response

For all the humoral assays the immune response values will be  $\log_{10}$ -transformed before any further handling. The  $\log_{10}$ -transformed values will be used throughout the analysis. In the graphs, original values will be displayed on the  $\log_{10}$  scale.

For each assay and at each time point geometric mean of actual values, geometric mean increases and percentage of responders, all with corresponding 95% CIs will be provided in the tables. Also, mean fold change from highest post-baseline value to week 72 will be reported. The definition of responders is defined in section 6.4 for each assay. Graphical presentations will be provided displaying dots for the subject values and including the geometric mean and the percentage of responders. If available, baseline values will be summarized pooling all the groups and will be displayed on the left of each graph. Data from post-baseline timepoints will be plotted next to each other for each group, a symbol will identify the geometric mean (or the median) of each group and timepoint.

In the graphs the actual values will be shown and the LLOQ cut-off will be visualized, the values below LLOQ or below LOD will be visualized with the value imputed as described in section 6.3.

Graphs by subgroups listed in section 2.4 will be done for Elisa Clade C (C97ZA.012), ADCP Clade C (C97ZA.012).

Durability will be shown as a line plots displaying the GM/median for each vaccine regimen.

Magnitude-breadth (MB) plot for the ELISA assay will be provided at each timepoint to explore the magnitude and breadth of each individual serum sample assayed (antibody titers of 5 Clades). MB curves will show, for each possible titer threshold, the proportion of antibody titers greater than this threshold. The group-specific curve obtained as the average MB across all subjects in that group will be displayed. The AUC-MB is calculated as the average of the titers over the panel of antigens.

For BAMA the median will be reported instead of the geometric mean. Cumulative number of responses across the IgG/antigen classes will be tabulated.

Magnitude-breadth (MB) plots for the BAMA assay will be provided at week 28 to explore the magnitude (MFI of IgG3 and of IgG breath binding antibodies) and breadth of each individual serum sample assayed. MB curves will show, for each possible MFI threshold, the fraction of antigens with MFI greater than this threshold.

Weights will be applied to take into account the correlation among the antigens (more details will be specified in the DPS).

The group-specific curve obtained as the average MB across all subjects in that group will be displayed. The AUC-MB is calculated as the average of the MFI over the panel of antigens.

### **Cellular response**

For ELISpot and for each peptide: n, median, quartile range, min, max of actual values, percentage of responders above a predefined threshold (see section 6.4) and corresponding 95% CI will be tabulated.

Graphical presentations will be provided displaying dots for the subject values and including the median and the percentage of responders. In the graphs the actual values will be shown and the LLOQ cut-off will be visualized, the values below LLOQ will be visualized with the value imputed as LLOQ/2.

In the graphs, original values will be displayed on the  $\log_{10}$  scale. Graphs by subgroups listed in section 2.4 will be done for ELISpot Env peptide pool PTE, Gag peptide pool PTE and Pol peptide pool PTE.

ICS

*T cells: CD4+, CD8+*

*Antigen: Combined pools and separated pools*

Cytokine counts: Marginal, Boolean AND (co-expression) counts, Boolean OR (and/or)

For CD4+ and CD8+ and for each antigen (combined and separated pools): n, median, quartile range, min, max, percentage of responders (see section 6.4) and corresponding 95% CI will be tabulated for each available cytokine background adjusted percentages listed below.

Cytokine (ISSCAT)	Description
CD154+	Marginal
GzB+	Marginal
ICOS+	Marginal
IFNg+	Marginal
IL2+	Marginal
IL17a+	Marginal
IL4+	Marginal
TNFa+	Marginal
IFNg+/IL2+	Boolean AND (co-expression)

Cytokine (ISSCAT)	Description
IFNg+/IL2+/TNFa+	Boolean AND (co-expression)
IFNg+/TNFa+	Boolean AND (co-expression)
IL2+/TNFa+	Boolean AND (co-expression)
IFNg+ or IL2+	Boolean OR (and/or)
IFNg+ or IL2+ or TNFa+	Boolean OR (and/or)

Graphical presentations will be provided displaying dots for the subject values and including the median and the percentage of responders. In the graphs the actual values will be shown and the LLOQ cut-off will be visualized, the values below LLOQ will be visualized with the value imputed as LLOQ/2.

In the graphs, original values will be displayed on the  $\log_{10}$  scale.

The technical details for the calculation of the cytokine background adjusted percentages to be displayed in the above described outputs will be outlined in the DPS.

Additional timepoints and tests within one of the above listed assays may be investigated for exploratory purposes. These data and data from timepoints belonging to the long-term extension part of the study will be analyzed using the approaches described above.

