An optional 2-year extension of this 3-year optional LTE is introduced in protocol amendment 3. Subjects will be informed of the option to participate in this 2-year extension at the next possible visit after approval of this amendment. Subjects willing to participate will need to sign the ICF appendix for the 2-year extension at Visit 23. Subjects not willing to participate in the 2-year extension will have their final study visit at Visit 23. For subjects willing to participate : As of protocol amendment 5, the LTE will be shortened by one year, so Visit 26 and Visit 27 have been removed and Visit 25 will be the final visit. Participants who already had their Visit 25 or Visit 26 will be contacted to perform an extra unscheduled exit visit, to be performed within 6 weeks after local approval of protocol amendment 5. This can be either a telephone call or an actual site visit and will need to include the same assessments as in the current Visit 25, except for the social impact questionnaire and blood sampling for HIV and immunogenicity testing. In case a safety issue (including a recent HIV exposure) emerges during the call, the participant might be asked to come to the site for further evaluation.

Subjects will attend follow-up visits at the clinic from Week 96 until the final visit at Week 216 (for subjects who consent to be followed-up for approximately 3 years after week 72) or Week 264 (for subjects who consent to be followed-up for approximately 4 years after week 72). Each visit includes recording of any SAEs, AESIs, and concomitant medications (any medication given in conjunction with an SAE, as well as any recurrent or chronic use of immunomodulators/suppressors and corticosteroids), and collection of samples for cellular and humoral immunogenicity assays.

Samples for HIV testing will be collected. In addition to an HIV-risk assessment, counseling related to avoidance of HIV infection, pre- and post-HIV test counseling will be provided to all subjects.

Also, at each visit, subjects will complete a social impact questionnaire ([Attachment 4](#)).

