**NOTE:**

a The start time of screening phase is 00:00. In case an earlier date is available (e.g. for lab or vital signs then use the very first date in order to include all data)

b In case a dose is not administered, the observations end up in the previous Follow-Up phase

c This timepoint is intended to be at the end of the main study i.e. Week 72. LTE data will be reported separately

For the immunogenicity analyses no phases will be constructed.

The periods/phases will be used primarily for safety and concomitant medication allocation. The post-dose periods (and the regimen phase) are considered active periods/phase, the screening and follow-up phases are considered non-active phases. There will be no phase defined for the LTE part of the study.

For descriptive statistics over time, assessments (regardless of the investigated parameter) will be allocated to an analysis visit based on the visit number as captured in the database.

For subjects that received a first dose, but did not receive a 2nd dose while still continuing their planned visit schedule, the measurements after the planned but not administered 2nd dose will not be included in graphs and tables showing descriptive statistics over time. Those measurements will be shown in listings but it will be indicated that these are not used in the analysis. Moreover, the vaccinations done after a missed one will not be shifted to the previous one but will be considered as planned: in the example above if the 2nd is missed, the 3rd vaccination will still be reported as post-dose 3.

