## 6. IMMUNOGENICITY

### 6.1. Analysis specifications

The analysis of immunogenicity will be done on the PPI analysis set (Section [2.3](#)).

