#### 6.4. Handling of Missing and/or Invalid Immune Response Data

Analysis will be carried out on the available data, no imputation will be done for missing samples.

BAMA and ICS unreliable values should be excluded from the analysis: those records will be flagged in the SDTM dataset.

LLOQs by assay/test are listed in section 6.5. Values below LLOQ or LOD will be handled as follows:

- Calculation of Geomean (humoral response except ADCP) and median (cellular response):
  - values < LLOQ are imputed =LLOQ/2
  - values = LOD are imputed =LLOQ/2
 For ADCP only:
  - values < LOD are imputed =LOD/2
- Calculation of fold increases from baseline:
  - values <LLOQ are imputed =LLOQ
  - values =LOD are imputed = LLOQ
 For ADCP only:
  - values < LOD are imputed =LOD

Values above the upper limit of quantification (ULOQ) will be handled as follows:

- Calculation of geomean and median:
  - Values>ULOQ are imputed=ULOQ.
- Calculation of fold increases from baseline:
  - Values >ULOQ are imputed with ULOQ

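### Long-term durability rests on per-visit summaries of whoever attended: the LTE analysis set is assigned to no immunogenicity output, and no within-subject decline is estimated after Week 72

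*SAP*

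**What the plan says.** **Method.** SAP 6.3 (Humoral response) states: "Durability will be shown as a line plots displaying the GM/median for each vaccine regimen". The same section plans "For each assay and at each time point geometric mean of actual values, geometric mean increases and percentage of responders, all with corresponding 95% CIs". Its last paragraph extends these methods to the LTE: "These data and data from timepoints belonging to the long-term extension part of the study will be analyzed using the approaches described above". BAMA and the cellular assays use medians instead of GMs.

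**Missing samples.** SAP 6.4: "Analysis will be carried out on the available data, no imputation will be done for missing samples".

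**Analysis set.** SAP 6.1: "The analysis of immunogenicity will be done on the PPI analysis set". SAP 2.3.3 defines an LTE set (PPI, Group 2A, at least one LTE visit), but no immunogenicity output refers to it. A note to SAP Table 3 says that LTE data are reported separately, without naming the set.

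**Decline measure.** The only one is in SAP 6.3: "mean fold change from highest post-baseline value to week 72 will be reported". No CI is stated for it, and nothing equivalent is named for later visits.

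**Who is observed.** Under Protocol 4.4 and 9.1.8, LTE entry is optional and needs its own consent at Week 72. Follow-up beyond Visit 23 (Week 216) needs a second consent. Subjects who decline stop there, so Week 264 is the last visit only "for subjects who consent to be followed-up for approximately 4 years after week 72".

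**Status and disclosure.** LTE durability is an exploratory objective and endpoint (Protocol 2.1.1 and 2.1.2). SAP 4.2 tabulates the number and percentage of subjects at each LTE visit.

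**The concern.** The line to Week 264 joins points that rest on different subjects. If SAP 6.1 is followed literally, points up to Week 72 use all Group 2A PPI subjects. Weeks 96 to 216 use those who agreed to enter the LTE, and Weeks 240 and 264 use those who agreed a second time. A reader will take the slope of that line as antibody decay. If those who stay have higher or lower titers than those who leave, part of the slope is a change of population.

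The per-visit CIs do not settle this, because they describe the level at each visit and not the change between visits. The geometric mean increase does not settle it either. For ELISA with a baseline below LLOQ, SAP 6.5 sets the increase to value/LLOQ, so for those subjects it is the level rescaled. How fast responses fall within a subject after Week 72, which is what the LTE was introduced to learn (Protocol 1.2), would have to be read off the figure by eye.

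**Working it through.** **1. The plan's own figure.** The documents give no sample size or precision for the LTE. The nearest figure is the main-study power in Protocol 11.3: a 1.5-fold difference, 100 against 50 evaluable subjects, SD 0.4 log10, 1-sided 5%, 80% power. Check: log10(1.5) = 0.176; SE = 0.4 × √(1/50 + 1/100) = 0.0693; 0.176/0.0693 − 1.645 = 0.897; power 81.5%. It reproduces. The SD of 0.4 and the n of 100 are carried forward below. Everything else is assumed.

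**2. Shift from a changing set.** If a share q leaves and stayers exceed leavers by D log10, the GM of those remaining lies q × D above that of the full group, with no change in any subject. For q = 10% to 50% and D = 0.1 to 0.4 the shift is 10^(0.1×0.1) = 1.02-fold to 10^(0.5×0.4) = 1.58-fold. Continuers lying 0.05, 0.10 or 0.15 log10 above the full group correspond to 10^0.05 = 1.12, 10^0.10 = 1.26 and 10^0.15 = 1.41. These inflate the Week 264/Week 72 ratio if the Week 72 point uses all Group 2A PPI subjects and the difference persists. For scale, the 95% CI factor of one visit's GM, 10^(t × 0.4/√n), is 1.20 at n = 100 and 1.34 at n = 40.

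**3. Simulated illustration.** Assumptions: 100 subjects, true decline of 0.40 log10 (2.51-fold) from Week 72 to 264, within-subject correlation 0.8, SD 0.4, and consent at Weeks 72 and 216 depending on the titer at that visit. Decline read from the ratio of visit GMs:

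| Consent odds ratio per SD | 90%/80% consent (72 left) | 80%/60% consent (48 left) |
|---|---|---|
| 1 | 2.51 | 2.51 |
| 1.5 | 2.31 | 2.10 |
| 2 | 2.18 | 1.93 |
| 3 | 2.04 | 1.71 |

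A random-intercept mixed model gave 2.49 to 2.52 throughout, with 95% CI coverage of 93% to 98%. Its linear time trend matched the simulated data, which were missing at random by construction. The result shows what such a model can do when its assumptions hold, not that they hold here.

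**4. Precision of the Week 264/Week 72 ratio.** Assume 100 subjects at Week 72, of whom 40 remain at Week 264. The 40 belong to the 100, so the covariance counts.

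- Ratio of available-data GMs: 10^(1.96 × √[0.16 × (1/100 + 1/40 − 2ρ/100)]) = 1.30, 1.28, 1.27 at ρ = 0.7, 0.8, 0.9.
- Paired within-subject ratio: 10^(1.96 × 0.4 × √[2(1−ρ)]/√40) = 1.25, 1.20, 1.14.

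The paired estimate is tighter, modestly so at ρ = 0.7.

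**The case against.** The strongest reply is that the plan suits its purpose. LTE durability is exploratory and no hypothesis is tested. Attendance is tabulated, individual values are plotted, and three quantities have CIs at each visit. An LTE set is defined, and using it for the whole curve would remove the step at Week 72. Eligibility adds little selection of its own: the LTE requires four doses and a negative HIV status, while the PPI set excludes HIV diagnoses and drops samples after Week 48 without a timely fourth dose. Protocol 16.2.4 says exploratory immunogenicity data are not returned to subjects or investigators, so there is no documented route by which titer would drive consent.

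Most of this stands and keeps the point minor. What remains is that the LTE set is not tied to the durability outputs. Even if it were, membership needs only one LTE visit, so the exit at Week 216 and missed visits would still change the curve. An attendance table shows how many left, not whether they differed.

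Three stronger readings are tempting and not supported:

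- **That the curve will overstate durability.** The documents do not relate uptake to titer. Direction and size are unknown, and the bias is zero if they are unrelated.
- **That nothing numeric on persistence is planned after Week 72.** The GM, geometric mean increase and responder rate with CIs carry over to LTE visits. Only a decline between visits is missing.
- **That the CI factor from separate GMs is 1.40**, from 10^(1.96 × √(0.16/100 + 0.16/40)). This treats the 40 as independent of the 100 and exaggerates the gain from pairing.

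Allocation "based on the visit number as captured in the database" (SAP 2.1) also ignores actual timing, but most LTE windows are ±4 weeks against 192 weeks (264 − 72), so this is secondary.

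**Conclusion.** The point holds as a cheap improvement to an exploratory analysis. The voluntary consent steps follow from the design, as do the unassigned LTE set and the absence of a within-subject decline after Week 72. Bias is only possible, not shown. An inflation of 1.12- to 1.41-fold needs continuers 0.05 to 0.15 log10 higher and a Week 72 point based on all Group 2A PPI subjects. The precision comparison (1.30/1.28/1.27 against 1.25/1.20/1.14) rests on the protocol SD, an assumed 40 of 100 remaining, and assumed correlations of 0.7 to 0.9. The Week 72 analysis is complete and will not be repeated, so only the LTE part is affected.

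**What to change.** In SAP 6.3:

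1. Assign the LTE set to the durability figures at all visits, including Weeks 52, 60 and 72. Print n under each point, and add a line for subjects with data through Week 264, because the LTE set itself changes after Week 216.
2. For Group 2A PPI subjects, add a repeated-measures mixed model on log10 ELISA and ADCP values. Fit visit as categorical, since a single slope from Week 52 may misfit. Treat values below LLOQ (ELISA) or LOD (ADCP) as censored. Report Week 216/Week 72 and Week 264/Week 72 GM ratios with 95% CIs.
3. Tabulate Week 72 titers of those who entered the LTE and those who did not, and Week 216 titers of those who continued and those who stopped. This checks directly whether continuers differ.

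The cost is a small amount of extra analysis on data already in the plan: one model, one redrawn figure and one table. The model assumes data are missing at random, which item 3 can make more or less plausible but cannot prove. The model covers all Group 2A PPI subjects and the figure covers the LTE set, so each should be labelled with its population.

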#### 6.4. Handling of Missing and/or Invalid Immune Response Data

Analysis will be carried out on the available data, no imputation will be done for missing samples.

BAMA and ICS unreliable values should be excluded from the analysis: those records will be flagged in the SDTM dataset.

LLOQs by assay/test are listed in section 6.5. Values below LLOQ or LOD will be handled as follows:

- Calculation of Geomean (humoral response except ADCP) and median (cellular response):
  - values < LLOQ are imputed =LLOQ/2
  - values = LOD are imputed =LLOQ/2
 For ADCP only:
  - values < LOD are imputed =LOD/2
- Calculation of fold increases from baseline:
  - values <LLOQ are imputed =LLOQ
  - values =LOD are imputed = LLOQ
 For ADCP only:
  - values < LOD are imputed =LOD

Values above the upper limit of quantification (ULOQ) will be handled as follows:

- Calculation of geomean and median:
  - Values>ULOQ are imputed=ULOQ.
- Calculation of fold increases from baseline:
  - Values >ULOQ are imputed with ULOQ

## 6.5. Immune response assays: details

The details for each immune response assay are listed in following table.

Assay	Test	Lab	LLOQ a	LOD a	ULOQ a	Unit	Responder definition (R)	Fold increase (FI) calculation
VNA	Ad26 VNA	Janssen Vaccines and Prevention	17	NA	NA	IC90	>LLOQ	NA
Env ELISA IgG-t gp140	Clade A (92UG037.1) Clade B (1990a) Clade C (Con C) Clade C (C97ZA.012) Mos1	Janssen Vaccines and Prevention	625 156.25 625 156.25 78.125	0	1600000 800000 1600000 400000 400000	EU/ml	1) if baseline <LLOQ or missing, R>LLOQ 2) if baseline >=LLOQ, R=3-fold increase from baseline	1) if baseline >LLOQ, FI=Value post-baseline/Value wk0 2) if baseline<LLOQ, FI=value post-baseline/LLOQ
Env ELISA IgG1,3	Clade C (C97ZA.012) IgG1 Clade C (C97ZA.012) IgG3	BIDMC	12.3 12.4	4	NA	EC50		
Env ADCP gp140	Clade A (92UG037.1) Clade B (1990a) Clade C (Con C) Clade C (C97ZA.012) Mos1	Ragon	NA	5.16 6.43 6.49 4.32 4.28	NA	PS	1) if baseline <LOD or missing, R>LOD 2) if baseline >=LOD, R=3-fold increase from baseline	1) if baseline >LOD, FI=Value post-baseline/Value wk0 2) if baseline<LOD, FI=value post-baseline/LOD
TZM-bl	Clade C (MW965.26) Clade C (C97ZA.012)	Duke U	20 20	NA	NA	ID50	>LLOQ	NA

a In case final LLOQ and ULOQ values present in the dataset differ from those listed in this table, those provided from the lab should be used.

Assay	Test	Lab	LLOQ a	LOD a	ULOQ a	Unit	Responder definition (R)	Fold increase (FI) calculation
BAMA IgG3	HIV ENV Con S gp140 CFI (Clade M) HIV ENV Con 6 gp120/B (Clade M) HIV ENV gp41 HIV ENV 1086C_D7gp120 (Clade C) HIV ENV 1086C gp140 (Clade C) HIV ENV 1086C_V1V2 (Clade C) HIV ENV gp70_B.Case A_V1V2 (Clade B)	Duke U	100 a	NA	NA	MFI	BAMA interpretation flag = 1	1) if baseline >LLOQ, FI=Value post baseline/Value wk0 2) if baseline<LLOQ, FI=value post baseline/LLOQ
BAMA Breadth	HIV ENV gp120 Clade A (51802) IgG-t Ab Clade AE (254008) IgG-t Ab Clade AE (A244) IgG-t Ab Clade B (B.6240) IgG-t Ab Clade B (BORI) IgG-t Ab Clade B (TT31P) IgG-t Ab Clade BC (CNE20) IgG-t Ab Clade BC(BJOX002) IgG-t Ab Clade C(1086C_D7) IgG-t Ab B Clade M (Con 6) IgG-t Ab  HIV ENV gp140 Clade B (SC42261) IgG-t Ab Clade C (CH505TF) IgG-t Ab C Clade A (9004S) IgG-t Ab C Clade B (RHPA) IgG-t Ab C Clade B (WITO) IgG-t Ab C Clade C (1086C) IgG-t Ab C Clade C (BF1266) IgG-t Ab CF Clade AE (conAE) IgG-t Ab							

a This is not LLOQ but “positive” threshold as provided by the lab

Assay	Test	Lab	LLOQ a	LOD a	ULOQ a	Unit	Responder definition (R)	Fold increase (FI) calculation
	CFI Clade M(Con S) IgG-t Ab  HIV ENV gp41 IgG-t Ab  HIV ENV gp70 Clade A (191084)IgG-t Ab Clade AE (C2101) IgG-t Ab Clade AE (CM244) IgG-t Ab Clade B (62357.14) IgG-t Ab Clade B (CaseA) IgG-t Ab Clade B (RHPA4259) IgG-t Ab Clade B (TT31P) IgG-t Ab Clade B(700010058) IgG-t Ab Clade BC (BJOX) IgG-t Ab Clade C (96ZM651) IgG-t Ab Clade C (BF1266) IgG-t Ab Clade C (CAP210) IgG-t Ab Clade C(Ce1086) IgG-t Ab Clade C(TV1.21)IgG-t Ab Clade C (001428)IgG-t Ab Clade C (7060101641)IgG-t Ab							
ELISpot	Env peptide pool Mos1 Pol peptide pool Mos1 Gag peptide pool Mos1 Env peptide pool Mos2 Pol peptide pool Mos2 Gag peptide pool Mos2 Env peptide pool PTE a (Env peptide pool 1 PTE, Env peptide pool 2 PTE, Env peptide pool 3 PTE)	BIDMC	55	0	NA	SFC/ $10^6$ PBMC	1) if baseline <threshold or missing, R>threshold 2) if baseline $\geq$ threshold, R=3-fold increase from baseline	73 b 112 87 70 63 55 100 NA

a ENV pep pool (PTE) will be provided split in pool 1,2,3: for the purpose of the statistical analysis they will be reported only as sum of the 3: HIV ENV pep pool. The ADAM should however contain also the 3 separated pools.

b Threshold for ELISpot test is based on the 95 percentile from the baseline values of about 350 subjects on that test in the HIV-V-A004 study

Assay	Test	Lab	LLOQ a	LOD a	ULOQ a	Unit	Responder definition (R)	Fold increase (FI) calculation
	Pol peptide pool PTE Gag peptide pool PTE						105 181	
ICS (CD4+, CD8+)	Combined pools HIV Gag pep pool HIV Pol pep pool (Mos1) HIV Env pep pool (Mos1) HIV Env pep pool clade C (ZA) HIV Env pep pool (Mos1 ZA) HIV Env Pol Gag pep pool  Separated pools HIV Pol RT pep pool (Mos1) HIV Gag pep pool (Mos1) HIV Pol RNaseInt pep pool 1 (Mos1) HIV Env gp120 pep pool 1 (Mos1) HIV Env gp41 pep pool 1 (Mos1) HIV Env gp120 pep pool clade C (ZA) HIV Env gp41 pep pool clade C (ZA)	FHCRC	NA	NA	NA	% of CD4+/CD8+ T cells	ICS interpretation flag=1	NA

NA: not applicable; PS: phagocytic score; SFC: spot forming cells, PBMC: peripheral blood mononuclear cell, MFI: median fluorescent intensities

